## **8.8. Benefit/Risk Assessment**

Patients may not expect to receive direct benefit from treatment during participation, as this study is designed to provide information about the safety and effectiveness of an investigational medicine compared to placebo. Some patients will receive tolterodine, an approved medication for treating overactive bladder with symptoms of urinary frequency, urgency, and leakage.

Additional details about vibegron may be found in the current vibegron Investigator's Brochure (IB) and Informed Consent documents.

## 9. STATISTICAL CONSIDERATIONS

This section contains a brief summary of the statistical analyses for this study; full details shall be provided in the Statistical Analysis Plan.

### 9.1. Responsibility for Analyses/In-House Blinding

The statistical analysis of the data obtained from this study will be the responsibility of the designee of the Sponsor.

The study will be conducted as a double-blind, Sponsor open (partially unblinded) study as described in Section 6.4.

At the end of the study (including the period of 28 days follow-up), the official, final database will be frozen and unblinded after medical/scientific review has been performed, and data have been declared final and complete. A Statistical Analysis Plan will be approved prior to data being unblinded. A clinical study report will be prepared after all patients complete the study.

### 9.2. Hypotheses

[figure not shown]
#### 9.2.1. Primary Objective and Hypotheses

The primary objective will be to demonstrate the long-term safety of vibegron 75 mg in patients with symptoms of OAB. There is no formal statistical primary endpoint hypothesis. Rather, incidence of treatment-emergent AEs by system organ class and preferred term will be descriptively summarized by treatment group based on study RVT-901-3004.

#### 9.2.2. Secondary Objectives

There are no formal statistical hypotheses for this trial. Below are the secondary efficacy objectives of this trial.

- (1) **Objective:** To evaluate the efficacy of vibegron in reducing the average number of daily micturitions from baseline at Week 52 in all patients with OAB.
- (2) **Objective:** To evaluate the efficacy of vibegron in reducing the average number of daily UI episodes from baseline at Week 52 in all patients with OAB.
- (3) **Objective:** To evaluate the efficacy of vibegron in reducing the average number of urgency episodes from baseline at Week 52 in all patients with OAB.

- 
- (6) **Objective:** To evaluate the efficacy of vibegron in reducing the average number of total urinary incontinence episodes from baseline at Week 52 in all patients with OAB Wet.

### 9.3. Analysis Endpoints

The descriptions of the endpoints and time points at which they are measured are described in Section 3 and Section 1.1 (Schedule of Activities), respectively.

No formal statistical comparisons of vibegron vs. tolterodine are planned. Any statistical analyses will be considered descriptive.

#### 9.3.1. Efficacy Endpoints

For the purpose of this study, the number of micturitions will be defined as the number of times a patient has voided in the toilet as indicated on the Voiding Diary. Average daily micturitions are calculated using the daily entries in the Voiding Diary, which is completed prior to each study visit. Average daily number of micturitions will be calculated as the total number of micturitions that occur on a Complete Diary Day divided by the number of Complete Diary Days in the Voiding Diary. A “Complete Diary Day” is defined as a Diary Day that includes input of micturition data by patients on the voiding diary. Unless a patient indicated “No” to the questions of “Did you record each time you urinated or leaked during this Diary Day”, the Diary Day is considered complete. Baseline is defined as the average number of micturitions occurring during the week of Run-in prior to the Baseline Visit in study RVT-901-3003. If data from the study RVT-901-3003 Run-in are not available for a patient, data collected during Screening will serve as the baseline.

[figure not shown]
The number of UUI episodes will be defined as the number of times a patient has checked "urge" as the reason for accidental urine leakage. Average daily urge urinary incontinence episodes at each study visit will be calculated in the same manner as described above for the micturition endpoint. The urge urinary incontinence endpoint will be analyzed using only OAB Wet patients.

[figure not shown]
Secondary Endpoints:

- Change from baseline (CFB) at Week 52 in average number of micturitions per 24 hours in all OAB patients
- CFB at Week 52 in average number of urge urinary incontinence (UUI) episodes per 24hours in OAB Wet patients

- CFB at Week 52 in average number of urgency episodes (need to urinate immediately) over 24 hours in all OAB patients
- CFB at Week 52 in average number of total urinary incontinence episodes over 24 hours in OAB Wet patients

Exploratory Endpoints:

### **9.3.2. Safety Endpoints**

Safety and tolerability will be assessed via clinical review of all relevant safety parameters including clinical adverse events, clinical laboratories, vital signs, and physical examinations that occurred during the respective study period.

## **9.4. Analysis Populations**

### **9.4.1. Efficacy Analysis Populations**

The Full Analysis Set Extension (FAS-Ext) population will serve as the population for the analysis of efficacy data in this study. Since the endpoints related to incontinence would only apply to patients who meet the definition of incontinence at study entry, it is necessary to have a separate FAS definition with an additional criterion to define the analysis population for incontinence endpoints.

The following FAS populations are defined in the study:

- Full analysis set extension (FAS-Ext): all OAB patients who took at least one dose of double-blind Study Treatment in the current study and have at least one evaluable change from baseline micturition measurement in this study
- Full analysis set extension for incontinence (FAS-Ext-I): all OAB Wet patients who took at least one dose of double-blind Study Treatment in the current study and have at least one evaluable change from baseline urge urinary incontinence measurement in this study

The Per-Protocol extension population (PP-Ext) and Per-Protocol extension population for incontinence (PP-Ext-I) exclude patients due to important deviations from the protocol that may substantially affect the results of the efficacy endpoints. A supportive analysis using the Per-

Protocol populations will be performed for the 4 key secondary efficacy endpoints. The final determination on protocol violations, and thereby the composition of the Per-Protocol population, will be made prior to the unblinding of the database and will be documented in a separate memo.

Patients will be included in the treatment group to which they are randomized to for the analysis of efficacy data using the Full Analysis Set and Per-Protocol populations. Efficacy endpoints will be descriptively summarized by treatment group based on treatment in both RVT-901-3003 and study RVT-901-3004. This means there will be 4 treatment groups including vibegron for 52 weeks, tolterodine for 52 weeks, vibegron for 40 weeks, and tolterodine for 40 weeks.

#### **9.4.2. Safety Analysis Populations**

The Safety Analysis (SAF) population will be used for the analysis of safety data in this study. The SAF population consists of all patients who received at least one dose of Study Treatment in this study. Patients will be included in the treatment group corresponding to the Study Treatment they actually received for the analysis of safety data using the SAF population. For most patients, this will be the treatment group to which they were randomized. Patients who take incorrect Study Treatment for the entire Treatment Period will be included in the treatment group corresponding to the Study Treatment actually received. Safety endpoints will be descriptively summarized based on treatment in study RVT-901-3004. This means there will be 2 treatment groups including vibegron (52 weeks and 40 weeks combined) and tolterodine (52 weeks and 40 weeks combined).

At least one laboratory or vital sign measurement obtained subsequent to at least one dose of Study Treatment is required for inclusion in the analysis of each specific parameter. To assess change from baseline, a Baseline measurement is also required.

No imputation will be performed for missing safety data. Baseline will be defined as the last non-missing value before double-blind treatment in study RVT-901-3003. Further inclusion of data from RVT-901-3003 in the reporting of this study will be described in the SAP.

### **9.5. Statistical Methods**

#### **9.5.1. Statistical Methods for Efficacy Analyses**

##### **Secondary Endpoints: Efficacy**

Statistical analysis of efficacy endpoints will be for descriptive purposes only. Baseline will be the RVT-901-3003 baseline. Further inclusion of data from RVT-901-3003 in the reporting of this study will be described in the SAP.

For the analysis of continuous change from baseline endpoints (e.g., change from baseline in average number of daily micturitions, change from baseline in average number of daily urge urinary incontinence episodes, change from baseline in average number of urgency episodes, and change from baseline in average number of total incontinence episodes), a mixed model for repeated measure (MMRM) with restricted maximum likelihood estimation will be used. This model corrects for dropout and accounts for the fact that measurements taken on the same patient over time tend to be correlated, by using all available information on patients within the same covariate set to derive an estimate of the treatment effect for a dropout-free population. The

analysis model for each efficacy endpoint will include terms for treatment, visit, baseline stratification factors (only those that were statistically significant in RVT-901-3003 will be included in the models), baseline score, and interaction of visit by treatment. Only patients on active treatment in both RVT-901-3003 and RVT-901-3004 will be included in the model.

Adjusted means and 95% confidence intervals will be presented for each visit and each treatment group. No p-values and no treatment differences will be presented.

An unstructured covariance matrix will be used to model the correlation among repeated measurements. The Kenward-Roger adjustment will be used with restricted (or residual) maximum likelihood (REML) to make proper statistical inference. If the unstructured covariance model fails to converge with the default Newton-Raphson algorithm, the Fisher scoring algorithm or other appropriate methods can be used to provide initial values of the covariance parameters. In the rare event that none of the above methods yield convergence, a structured covariance will be used to model the correlation among repeated measurements.

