	
Study visits will be named to reflect continuation from the RVT-901-3003 study, with the first study visit of this extension study occurring at Study Treatment Week 12. Following enrollment in this extension study, patients will return to the clinic for visits at Week 16, Week 24, Week 36, Week 44, and Week 52 (all relative to Day 1 of RVT-901-3003). The Schedule of Activities (Section 1.1) summarizes the assessments/procedures to be performed at each visit.
 
This study consists of a randomized double-blind Treatment Period (40 weeks), and a Safety Follow-up Period (4 weeks). All patients will have a Follow-up Visit approximately 28 days after the patient’s last dose of study treatment (i.e., at Week 56 for patients who complete the Week 52 Visit, or approximately 4 weeks after withdrawal for patients who discontinue the study early). Additionally, unscheduled follow-up visit(s) may be arranged for patients with study-related safety concerns as needed.

Study Treatments
	
The investigator, site staff, and the patients will remain blinded to the Study Treatment during this extension study.
 
All treatments are dosed orally, once daily (QD). Patients will receive one of the following blinded treatments:
 
 
• Vibegron 75 mg tablet + placebo capsule to match tolterodine ER 4 mg capsule (N = 267)
 
• Tolterodine ER 4 mg capsule + placebo tablet to match vibegron 75 mg tablet (N = 233)
 
 
All patients previously randomized to placebo in RVT-901-3003 will be randomized 1:1 to receive vibegron 75 mg tablet + placebo capsule to match tolterodine ER 4 mg capsule or tolterodine ER 4 mg capsule + placebo tablet to match vibegron 75 mg tablet, in this extension study.

Duration of Treatment
	
40 weeks
 
Note: upon entering this extension study, all patients will have already received 2 weeks of treatment with placebo plus an additional 12 weeks of treatment with vibegron, tolterodine, or placebo in the RVT-901-3003 study.

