**Patient Voiding Diary and Urine Volume Diary**

6. Specific re-training on completion of the Voiding Diary and Voided Volume Diary will be provided to the patient at each visit.
7. The Voiding Diary should be completed by the patient on all of the 7 Diary Days prior to the Week 16, 24, 44, and 52 Visits. Patient will receive an alert and/or phone call reminder to complete the diary.
8. The Voided Volume collection and Voided Volume Diary completion should be performed by the patient on one (1) of the 7 Diary Days prior to the Weeks 16, 24, 44, and 52 Visits.

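### The efficacy MMRM forces one baseline slope on every visit; a baseline-by-visit term would guard the Week 52 adjusted means at almost no cost (low severity)

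*Protocol*

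**What the plan says.** Protocol Section 9.5.1 and the Efficacy paragraph of the synopsis give the same term list for the MMRM: treatment, visit, selected stratification factors, "baseline score, and interaction of visit by treatment". Treatment is allowed to act differently at each visit; the baseline score is not.

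Section 9.5.1 also states:

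- the purpose of the model: "This model corrects for dropout", aiming at an estimate for a population without dropout;
- the covariance: "An unstructured covariance matrix will be used to model the correlation among repeated measurements";
- the patients: "Only patients on active treatment in both RVT-901-3003 and RVT-901-3004 will be included in the model";
- the output: "Adjusted means and 95% confidence intervals will be presented for each visit and each treatment group", and "No p-values and no treatment differences will be presented".

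Footnote 7 of the Schedule of Activities has the voiding diary completed "on all of the 7 Diary Days prior to the Week 16, 24, 44, and 52 Visits", so the extension supplies four diary visits. Sections 9.3 and 9.6 make all efficacy analysis descriptive.

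**The concern.** An MMRM handles missing-at-random dropout by using each patient's baseline and earlier visits to inform the visits that are missing. That works only if the mean at each visit is modelled correctly. With one baseline slope, the relation between baseline severity and change is assumed identical at Weeks 16, 24, 44 and 52. If that relation shifts over the 36 weeks between the first and last diary visit, and patients with worse baseline scores leave at a different rate, the Week 52 mean is adjusted with the wrong slope.

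The arm-level Week 52 adjusted means and their intervals are at stake. They are the model-based result for the four secondary endpoints. A common shift would normally drop out of a treatment difference, but this plan presents no difference, so the shift would stay in every number that is shown.

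**Working it through.** **Nothing to reproduce.** The protocol states no power, effect size, SD, baseline slope or dropout rate for this model. The check therefore asks when a bias arises and how large it is over an assumed range.

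**Inputs from the protocol.** The model terms; four diary visits; only patients on active drug in both studies; planned totals of 267 (vibegron) and 233 (tolterodine) in the synopsis, each combining 52-week and 40-week patients.

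**Group sizes (assumed split).** If the former vibegron and placebo groups are equal in size, V + V/2 = 267 gives V = 178. The 52-week tolterodine group is then 233 − 89 = 144. Check: 178 + 178 + 144 = 500.

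**Other assumed inputs.** Baseline SD 4, residual SD 3, within-patient correlation 0.6, dropout by Week 52 of 15% or 30%, and odds of leaving per visit interval multiplied by 1.0, 1.5 or 2.5 per SD of higher baseline.

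**Why two conditions are needed.** Let the true mean change at visit j be μ_j + β_j(b − b̄), and let β be the single fitted slope. Using the patients still observed at Week 52, the error in the adjusted mean is roughly

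(β_52 − β) × (b̄_observed − b̄).

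It vanishes if the slope is constant (first factor) or if dropout is unrelated to baseline (second factor).

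Example: slopes −0.30, −0.36, −0.44, −0.50 average −1.60/4 = −0.40. With 30% dropout and odds ratio 2.5, the observed baseline mean at Week 52 was 0.26 SD low, that is −0.26 × 4 = −1.04. The rough error is (−0.50 + 0.40) × (−1.04) = +0.10. The full model gives more (+0.15). Its fitted slope leans towards the earlier, fuller visits, and it carries early residuals of the leavers, distorted by the common slope, forward to Week 52. A positive sign means that the reduction is understated; drift in the other direction would reverse it.

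**Large-sample bias of the Week 52 adjusted mean, single slope** (100,000 patients per arm, approximate average of the arms, episodes/day):

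| Slope, Week 16 to Week 52 | 15% dropout, OR 1.5 | 30% dropout, OR 2.5 |
|---|---|---|
| −0.40 constant | 0 | 0 |
| −0.36 to −0.44 | +0.02 | +0.07 |
| −0.30 to −0.50 | +0.04 | +0.15 |
| −0.20 to −0.60 | +0.07 | +0.31 |

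Monte Carlo error is about 0.02. With baseline-by-visit added, the bias was within that error of zero wherever baseline drove dropout. At OR 1.0 the two models agreed to within 0.01 for every slope pattern.

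**At 178/144 patients (300 replicates, vibegron).** Single-slope mean minus by-visit mean, in the row order of the table:

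- 15%, OR 1.5: 0.00, 0.01, 0.04, 0.07.
- 30%, OR 2.5: 0.00, 0.06, 0.16, 0.31.

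At 30% and OR 2.5, coverage of the single-slope 95% CI was 89% for −0.30 to −0.50 and 77% for −0.20 to −0.60, against 95% with the interaction in both cases. At 15% and OR 1.5 it stayed between 93% and 96%. Monte Carlo error of a coverage figure is √(0.95 × 0.05/300) ≈ 1.3 percentage points.

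**Cost in precision.** With a constant slope, the SE went from 0.235 to 0.235 (15%) and from 0.249 to 0.252 (30%). Under the strongest drift at 30% it fell from 0.264 to 0.252.

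**Between-arm difference.** The same under both models to within 0.003.

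**Second set of assumed inputs.** With 180 per group, SD 2.5, about 18–19% dropout and drift of 0.10 to 0.20, the bias was 0.017 to 0.078 micturitions/day. Against an SE of about 0.2, that is 0.017/0.2 ≈ 0.09 to 0.078/0.2 = 0.39 of an SE. It was under 0.01 with the interaction.

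**Limits.** The table and the 178/144 runs used maximum likelihood, not REML with Kenward-Roger, and no stratification factors. The smaller OAB Wet set used for the two incontinence endpoints was not simulated separately.

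**The case against.** The strongest reply is that this is a preference. A baseline main effect is a conventional MMRM specification, nothing in the protocol contradicts it, and Section 9 calls itself a summary with details to follow in the SAP, which may already hold the extra term. The analysis is descriptive and no decision rests on it. Neither condition has support in the document: no slope or dropout figures are given. Patients also entered after 12 completed weeks with at least 80% compliance, so much of the early response and regression to the mean may precede Week 16.

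Most of this stands, and it is why the point is graded low. It does not remove the point: the term list is stated twice, so this is a stated method with a better one available, and the better one costs almost nothing if it proves unnecessary.

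Three stronger readings are tempting and not supported:

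- *Selective dropout by severity biases the planned model by itself.* It does not. With a constant slope the bias was zero within simulation error even at 30% baseline-driven dropout.
- *The comparison of vibegron with tolterodine is distorted.* The shift is nearly the same in both arms; a reader who subtracts the two adjusted means gets the same contrast under either model.
- *The unstructured covariance shows that the plan meant to leave the mean time course free.* Section 9.5.1 uses it for the correlation among measurements; the time course of the means is freed by visit and visit-by-treatment.

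**Conclusion.** The point holds as a low-severity improvement. The stated MMRM imposes one baseline slope on all visits. The arm-level Week 52 adjusted means are biased, and their intervals can under-cover, only if the slope of change on baseline differs between visits and dropout depends on baseline severity. The true size cannot be known from the protocol and may be zero. Over the assumed range it is 0 to about 0.3 episodes per day. It exceeds one SE only in the most extreme case (0.31/0.264 ≈ 1.2), and marked loss of coverage appeared only with 30% strongly baseline-driven dropout and a slope drift of 0.20 or more. No trial conclusion depends on it: the primary objective is safety and the efficacy results are descriptive.

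**What to change.** In Section 9.5.1 and the synopsis, add the baseline-score-by-visit interaction to the MMRM term list for the four secondary endpoints, and carry it into the SAP before unblinding if it is not already there.

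The cost is one model term and no new data. It uses 3 degrees of freedom if the four extension diary visits are modelled; Section 9.5.1 leaves the use of RVT-901-3003 data to the SAP, so the number changes if parent-study visits are included. The SE increase in the simulations was at most 0.003.

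The term guards against this one source of bias. It does not address dropout that depends on outcomes nobody observed, and the text should not suggest that it does.

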### **9.5.2. Statistical Methods for Safety Analyses**

Safety analyses will be conducted using the safety population and summarized by treatment group as treated. The treatment-emergent period will be defined as the period of time from the first dose date of the double blinded Study Treatment in this study through 28 days after the last dose of Study Treatment, or the date of initiation of another investigational agent or surgical intervention, whichever occurs first. Safety will be assessed through summaries of adverse events, the frequency of treatment discontinuations due to adverse events, and clinical laboratory evaluations.

The severity of all adverse events will be evaluated by the Investigator as described in Section 8.5. All adverse events will be coded to preferred term and system organ class using MedDRA 20.0 or higher. The incidence of adverse events will be presented by MedDRA system organ class and preferred term, relationship to Study Treatment, and severity.

Laboratory data will consist of chemistry, hematology, and urinalysis data. Only data collected by the central laboratory will be included in the analyses.

Vital signs parameters, including temperature, will be listed and summarized by visit.

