**Adverse Events**

15. Adverse Events will be collected from the time a patient takes the first dose of Study Treatment in the RVT-901-3004 study until the Follow-up Visit is completed.

16. Serious Adverse Events will be collected from the time a patient takes the first dose of Study treatment in the RVT-901-3004 study until the Follow-up Visit is completed.

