### **5.5. Withdrawal from the Study**

Patients may withdraw consent at any time for any reason or be withdrawn from the study at the discretion of the Investigator should any untoward effect occur. Every effort should be made to establish and document the possible reasons for withdrawal. A patient may be withdrawn by the Investigator or the Sponsor if enrollment into the study is inappropriate, the study plan is violated, or for administrative and/or other safety reasons. The patient may be discontinued from further study participation after discussion between the Investigator and the Sponsor clinical monitor (or designee) if the patient requires therapy with any excluded medication. Medications that may cause a patient to be discontinued have been described in Section 7.7.3.

A patient must be discontinued from the study for any of the following reasons:

- The patient or legal representative (such as a legal guardian) withdraws consent.
- Study treatment administration is interrupted for more than 21 consecutive days.
- The patient has a medical condition or personal circumstance which, in the opinion of the Investigator and/or Sponsor, places the patient at unnecessary risk through continued participation in the study or does not allow the patient to adhere to the requirements of the protocol.
- The patient has a confirmed positive serum pregnancy test.
- The patient is unable to complete the study procedures successfully, including completion of the Patient Voiding Diary.

When a patient withdraws from the study prior to study completion, all applicable activities scheduled for the Week 52 Visit should be performed at the time of withdrawal. Any adverse events that are present at the time of withdrawal should be followed in accordance with the safety requirements outlined in Section 8.

Once a patient is withdrawn, he/she shall not be allowed to enroll again.

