## **7.17. Adverse Events**

Spontaneously reported adverse events will be recorded at each visit. The Investigator or site staff is responsible for detecting, documenting, and reporting events that meet the definition of an adverse event or serious adverse event. See Section 8 for details on adverse event definitions and reporting.

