- Medical or surgical procedure (e.g., endoscopy, appendectomy) should be entered into the electronic case report form (eCRF). If not planned prior to signing the informed consent, the condition that leads to the procedure is reported as an adverse or serious event, as appropriate. Periodic procedures for routine maintenance of a medical device

should not be considered associated with an adverse event (e.g., expected change of a stent);

- Situations where an untoward medical occurrence did not occur (e.g., planned hospitalization for an elective procedure, with elective defined as known or planned at the time of signing of the informed consent; social and/or convenience admission to a hospital);
- Anticipated day-to-day fluctuations of pre-existing disease(s) or condition(s) present or detected at the start of the study that do not worsen.

Adverse events that occur during the study should be evaluated by the Investigator and assessed for causal relationship to Study Treatment and severity, as described in Section 8.4 and Section 8.5. Episodic adverse events, such as vomiting, or those that occur repeatedly over a period of consecutive days are “intermittent”. All other events are “continuous”. Additional information on detecting, documenting, and reporting adverse events and serious adverse events are provided below. No toxicity-related dose reductions of Study Treatment are permitted; however, Study Treatment can be held for a period of up to 21 days for evaluation and treatment of an adverse event. The Study Treatment may be restarted if deemed safe for the patient by the Investigator.

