### 8.3.1. Period for Reporting Adverse Events

Adverse events and serious adverse events will be collected from the time a patient takes the first dose of Study Treatment in the RVT-901-3004 study until the Follow-up Visit is completed approximately 28 days after the last dose of Study Treatment or the date of initiation of another investigational agent, an alternate therapeutic drug for overactive bladder, or surgical intervention for overactive bladder, whichever occurs first. Events that occurred prior to the patient taking to the first dose of Study Treatment in the RVT-901-3004 study but after the patient provided informed consent to participate in the RVT-901-3003 study will be reported under the RVT-901-3003 study. Serious adverse events reported to the Investigator after the safety reporting period should be reported to the Sponsor if the Investigator assesses the event as related to Study Treatment.

Reporting instructions for serious adverse events are provided in Section 8.3.2.

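### Sections 9.5.2, 8.3.1 and Schedule of Activities footnotes 15-16 set three different windows for the adverse events behind the only primary endpoint

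*Protocol*

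**What the plan says.** Section 9.2.1 sets no hypothesis for the primary objective. Instead, "incidence of treatment-emergent AEs by system organ class and preferred term will be descriptively summarized by treatment group". Which events qualify depends on the following texts.

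- **Counting (9.5.2).** This is the only definition of the treatment-emergent period. It runs from the first extension dose through 28 days after the last dose, "or the date of initiation of another investigational agent or surgical intervention, whichever occurs first".
- **Collection (8.3.1).** AEs and SAEs are collected from the first extension dose until the Follow-up Visit, or until another investigational agent, "an alternate therapeutic drug for overactive bladder, or surgical intervention for overactive bladder, whichever occurs first". After that period, only SAEs assessed as related are reported.
- **Collection (Schedule of Activities, footnotes 15 and 16).** AEs and SAEs are collected from the first dose "in the RVT-901-3004 study until the Follow-up Visit is completed". No event closes collection early.

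The introduction to Section 9 describes the section as a brief summary and adds that "full details shall be provided in the Statistical Analysis Plan".

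**The concern.** The texts disagree in two directions.

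**Collected but not counted.** The surgery trigger in 9.5.2 is unqualified, whereas 8.3.1 restricts it to surgery for overactive bladder. Taken literally, a patient who has an unrelated operation and stays on study drug keeps reporting events, but new ones no longer enter the treatment-emergent tables. The protocol foresees such operations. Section 8.1 says: "Medical or surgical procedure (e.g., endoscopy, appendectomy) should be entered into the electronic case report form". Surgery is not among the mandatory discontinuation reasons in 5.5. The nearest one is a long pause in dosing ("Study treatment administration is interrupted for more than 21 consecutive days"), which a short operation need not cause.

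**Counted but not collected.** An alternate OAB drug closes collection under 8.3.1 but does not close the window in 9.5.2. Between the start of that drug and the end of the window, events belong in the tables, yet a site following 8.3.1 need not record them. A site following footnotes 15-16 would.

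The primary objective is long-term safety, so on-drug time late in the study is what the extension adds. The SAP could correct the first problem without loss of data. It cannot recover events that were never recorded.

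**Working it through.** **Side by side: does the event close the window?**

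| Event | 9.5.2 (counting) | 8.3.1 (collection) | Footnotes 15-16 (collection) |
|---|---|---|---|
| Another investigational agent | yes | yes | no |
| Surgery for OAB | yes | yes | no |
| Surgery not for OAB | yes, read literally | no | no |
| Alternate OAB drug | no | yes | no |
| Normal end | 28 days after last dose | Follow-up Visit | Follow-up Visit |

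No two columns agree.

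**Length of the window for a completer.** Inputs: dosing starts at the Week 12 Visit, Study Day 85 (4.2 and Schedule of Activities), and the last dose is on Day 364 (4.2).

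- On-drug days: 364 − 85 + 1 = 280.
- Window end: 364 + 28 = Day 392.
- Window length: 392 − 85 + 1 = 308 days.

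**Effect of unrelated surgery on one patient,** counting the surgery day as inside the window:

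- Day 169 (Week 24): 392 − 169 = 223 days lost (72% of 308), of which 364 − 169 = 195 are on drug.
- Day 253 (Week 36): 392 − 253 = 139 days lost (45%), of which 364 − 253 = 111 are on drug.

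**Effect on group incidence.** The documents give no surgery rate and no AE rate, so both are assumptions. Let a term have true incidence p over the 308 days with constant daily hazard λ = −ln(1 − p)/308. Let surgery fall evenly on days s = 85 to 364. A patient with surgery on day s contributes 1 − exp[−λ(s − 84)]. The average over s is 2.30% for p = 5% and 4.66% for p = 10%. The loss per affected patient is therefore 5 − 2.30 = 2.70 and 10 − 4.66 = 5.34 percentage points. Multiplying by the assumed share with unrelated surgery, and by the 267 planned vibegron patients (Synopsis):

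| Share with unrelated surgery | 5% term: points lost (patients of 267) | 10% term: points lost (patients of 267) |
|---|---|---|
| 1% | 0.03 (0.07) | 0.05 (0.14) |
| 5% | 0.13 (0.36) | 0.27 (0.71) |
| 10% | 0.27 (0.72) | 0.53 (1.43) |

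This takes everyone to Day 364. With dropout there would be less time to lose.

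**New OAB drug.** If one starts on Day 364, Days 365 to 392 (28 days) lie inside the 9.5.2 window but outside 8.3.1 collection. The gap is longer if the drug starts while study treatment continues. Section 7.7.3 leaves that open, since it says only that a prohibited therapy may require stopping study treatment. The documents give no basis for a rate of such switches, so I put no figure on the change in incidence.

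**Follow-up Visit against window end.** The visit is Day 393 ± 3, so Days 390 to 396. At Day 390 it falls 2 days before the window ends on Day 392. Collection to the visit therefore does not always cover the whole window.

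**The case against.** The strongest reply is that 9.5.2 is a shortened copy of 8.3.1. It follows the same order of events and the same closing phrase, and nothing suggests an intent to discard on-drug events after, say, an appendectomy. Section 9 is a summary, and the SAP is to be approved before unblinding. This stands as an account of how the wording arose, and it makes the counting problem easy to repair. It does not answer the collection problem, which sits in Section 8 and governs what sites record.

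It can also be said that little is lost after a new OAB drug. Section 7.22 still gathers serious events at the Follow-up Visit, 8.3.1 still takes related late SAEs, existing events are followed to resolution, and Table 3 bars the listed OAB drug classes during the study. That also stands. What remains exposed is mainly new non-serious events, mostly in the weeks after the last dose. Ending collection at a new OAB drug is itself a defensible choice, because later events are confounded. The defect is that collection and counting follow different rules.

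Two stronger readings are tempting but unsupported. A reader might take 7.17 ("Spontaneously reported adverse events will be recorded at each visit") as a further conflict, but that section refers to Section 8 for reporting details. A reader might also infer from the background on tolterodine discontinuation that the gap differs between groups. That background makes no comparison with vibegron, and entry here requires completion of RVT-901-3003 with at least 80% compliance. The documents show no between-group difference.

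**Conclusion.** The inconsistency is real and bears on the only primary endpoint. Followed as written, the protocol leaves out of the tables some on-drug events that it collects, and counts a period in which 8.3.1 does not require collection.

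For an affected patient the first effect can be large: 223 of 308 days for surgery on Day 169. On average it is probably small, at 0.03-0.27 percentage points for a 5% term and 0.05-0.53 for a 10% term. Those figures rest on the literal reading of 9.5.2, an assumed 1-10% unrelated-surgery rate, even timing, constant hazard and full follow-up. The second effect cannot be sized from the documents. The endpoint is descriptive, so no test or error rate is affected. The point should be fixed because the correction is cheap and uncollected events cannot be restored; the documents do not support a claim that the safety conclusions are biased.

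**What to change.** 1. In 9.5.2, qualify the surgery trigger as surgery for overactive bladder, matching 8.3.1, so that unrelated surgery does not close the window.
2. Reconcile 9.5.2, 8.3.1 and footnotes 15-16 so that one set of closing events governs both collection and counting, with one stated rule for an alternate OAB drug.
3. State that AEs and SAEs are collected through the whole treatment-emergent period, which is 28 days after the last dose unless an agreed event closes it, even if the Follow-up Visit falls earlier within its ±3-day window.
4. If events after a new OAB drug are kept, flag them in the data.

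The cost is a few words in three places, made through an amendment that needs IRB/REB/IEC approval under 10.6. A few more events may be collected and counted. No visit or summary table is added, though an early Follow-up Visit would need a way to capture the remaining day or two.
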